4.7.3 Laboratory Data

Descriptive summaries of laboratory values at screening, run-in, randomization, and during the 52-week double-blind treatment period, including changes from the randomization visit, will be generated for hematology, chemistry, and urinalysis parameters. The proportion of patients with values outside the normal upper and lower limit at each visit will be calculated overall and by change from the randomization visit. In addition, selected lab parameters (including, but not limited to, AST, ALT, alkaline phosphatase, total bilirubin, hemoglobin, and absolute neutrophil count) will be summarized by grade using the WHO grading scale (2003).

The number and percentage of patients with positive serum antibodies against MSTT1041A at baseline and during the 52-week double-blind treatment period will be tabulated. The relationship between ADA status and safety, efficacy, PK, and biomarker endpoints will be explored.

4.7.4 ECG Results

The number and percentage of patients with abnormal ECG findings at screening, run-in (Week 0), randomization (Week 2), Week 4, Week 26, and Week 54 will be summarized.

In addition to the primary investigator, a separate agency (Cardiocore through Vitalograph) will review all ECG's independently. ECG findings that change from normal to abnormal or an abnormality to a different abnormality will be analyzed and summarized.

For corrected QT interval using Fridericia's method (QTcF), PR, and QRS intervals as well as heart rate, the values at each timepoint as well as changes from randomization will be summarized descriptively. The difference in mean QTcF change from randomization between each MSTT1041A arm and placebo and the corresponding 2-sided 90% CI will be summarized for Week 26 and Week 54.

The proportion of patients who experience a QTcF value >450, >480, or >500 ms for males or >470, >490, or >510 ms for females at a given visit, or an increase from randomization in QTcF of >30 and >60 ms will be summarized. The proportion of

patients who experience a QTcF value > 450 ms for males or > 470 ms for females, or a QTcF increase from baseline of > 30 ms at any time during the study will be summarized.

In the event that a patient has more than three valid ECG records per visit, only the last three readings (by timestamp) will be analyzed. For example, if a patient has four valid ECG records for the screening visit, only readings two through four will be analyzed, and the first reading will be ignored.

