3.3.2 Rationale for MSTT1041A Dose and Schedule

To assess the most appropriate dose of MSTT1041A in this population of patients with asthma, three MSTT1041A arms (70 mg, 210 mg, or 490 mg) and one placebo arm are proposed for this Phase IIb study. Treatment will be given Q4W for 1 year, for a total of 13 doses. Each dose will consist of four SC abdominal injections of MSTT1041A and/or matching placebo. The selection of doses and regimens was determined by three factors: achieving an efficacious clinical response, providing a broad range of exposures to assess the dose-response relationship, and ensuring patient safety.

[REDACTED]

The selected Phase IIb doses (70, 210, and 490 mg) are well within the dose range previously evaluated in Phase I studies. In Phase I studies, 700 mg of MSTT1041A was administered intravenously as a single dose and on a Q4W regimen (3 doses). In addition, 560 mg of MSTT1041A was administered subcutaneously as a single dose, which consisted of four SC abdominal injections (four 2-mL injections, for a total of 8 mL). Both doses were well tolerated, and no significant safety issues were identified.

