5.1.1.5 Metabolic or Cardiovascular Effects

Published studies involving mouse models of cardiovascular disease or in vitro culture systems describe potential cardioprotective and atheroprotective roles of the IL-33/ST2 axis (Sanada et al. 2007; Miller et al. 2008; Seki et al. 2009; McLaren et al. 2010; Wasserman et al. 2012). However, studies with conflicting data exist (Abston et al. 2012; Demyanets et al. 2013; Martin et al. 2015). In nonclinical toxicology and safety pharmacology studies with cynomolgus monkeys, no biologically significant changes were exhibited by MSTT1041A.

There is evidence supporting use of the soluble form of the ST2 receptor (sST2) as a prognostic biomarker of cardiovascular disease outcome (Sabatine et al. 2008; Shah and Januzzi 2010; Weir et al. 2010). Although published findings suggest a possible risk of exacerbation of existing cardiovascular disease in humans, there are no identified cardiovascular risks associated with inhibiting the IL-33/ST2 axis in humans.

Patients with certain forms of cardiovascular disease will be excluded from the study. To observe for any immediate cardiovascular toxicity, ECGs will be monitored (in triplicate). In addition, fasting glucose, HbA_{1c}, and lipid panels will be monitored to observe and/or identify any effects of MSTT1041A on cardiovascular risk factors.

During the study, investigators and healthcare professionals administering MSTT1041A should accurately report all Major Adverse Cardiac Events (MACE) on the Adverse Event eCRF, as instructed in Section 5.2 and Section 5.3, and should report these events immediately to the Sponsor as SAEs if appropriate. Major Adverse Cardiac Events include death due to cardiovascular causes, non-fatal myocardial infarction, non-fatal stroke or transient ischemic attack (TIA), unstable angina or chest pain requiring hospitalization, coronary revascularization, and congestive heart failure (CHF) requiring hospitalization.

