Appendix 1 Schedule of Activities (cont.)

ACQ = Asthma Control Questionnaire; ACQ-7 = Asthma Control Questionnaire (7 items); ACQ-5 = Asthma Control Questionnaire (5 items); AQLQ = Asthma Quality-of-Life Questionnaire; BMI = body mass index; CGIC = Clinician Global Impression of Change; CT = computed tomography; ECG = electrocardiogram; eCRF = electronic case report form; eDiary = electronic Diary; EoS = End-of-Study; ET = early termination; EQ-5D = EuroQol 5-Dimension Questionnaire; FeNO = fractional exhaled nitric oxide; HbA1c = hemoglobin A1c; HbsAg = hepatitis B surface antigen; HbsAb = hepatitis B surface antibody; HbcAb = hepatitis B core antibody; HCV = hepatitis C virus; IgE = Immunoglobulin E; PCR = polymerase chain reaction; PGIC = Patient Global Impression of Change; PK = pharmacokinetic; PPD = purified protein derivative; PRO = patient-reported outcome; Q4W = every 4 weeks; QFT = QuantiFERON[®] test; Rand. = randomization; RBR = Roche Biosample Repository; SC = subcutaneous; Screen = screening; SGRQ = St. George's Respiratory Questionnaire; TB = tuberculosis; UV = unscheduled visit; WGS = whole genome sequencing.

Notes: On treatment days, all assessments should be performed prior to dosing, unless otherwise specified.

Patients who are unable to tolerate study drug will discontinue study drug but should continue follow-up for all other study procedures and measurements through the end of the study.

^a The screening period may be between 12 and 28 days after study consent, as described in Section 4.5.2.

^b The run-in visit should be scheduled 2 weeks (± 5 days) prior to the randomization visit.

^c Patients who are randomly allocated into the 52-week double-blind treatment period but discontinue study drug should continue follow-up for all other study procedures and measurements through the end of the study. Patients who discontinue from the study prior to Week 50 should return to the site for an early termination visit 4 weeks (± 5 days) after the last dose of study drug and then enter the safety follow-up period.

^d Patients who experience symptoms consistent with an asthma exacerbation as defined in Appendix 12 will be asked to come to the clinic for an unscheduled visit. Patients will be asked to bring a urine sample and will undergo additional evaluations.

^e Visit windows are relative to randomization visit.

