Eligible patients were randomized in a 1:1:1:1 ratio to receive MSTT1041A at one of three doses (70, 210, or 490 mg) or placebo. Enrollment caps were utilized to ensure adequate power for biomarker subgroup analysis based upon blood eosinophil status at visit 1 (≥ 300 , < 300 cells/ μ L). The randomization was conducted such that approximately 30 patients per arm will have eosinophil-high status and approximately 95 patients per arm will have eosinophil-low status. Study drug is administered as four SC abdominal injections at the randomization visit (Week 2), Week 6, and every 4 weeks thereafter through Week 50.

[figure not shown]
Safety and efficacy, as well as pharmacokinetic (PK) and pharmacodynamic (PD) measures, are assessed throughout the double-blind treatment period, as described in the protocol and detailed in the Schedule of Assessments (see [Appendix 2](#)). The primary efficacy endpoint is the incidence of asthma exacerbations during the 52-week double-blind treatment period (Week 2 through Week 54).

All patients will be followed for 20 weeks after the last dose of study treatment. The 20 weeks include 4 weeks after the final dose in the double-blind treatment period and 16 weeks in the safety follow-up period. Assessments for the safety follow-up period are detailed in the Schedule of Assessments (see [Appendix 2](#)).

All patients who discontinue study drug early during the double-blind treatment period are asked to continue with the study assessments in the double-blind treatment period and then complete the safety follow-up period. Patients who are unable or unwilling to continue with assessments in the double-blind treatment period complete an early termination visit and then enter the safety follow-up period.

The study design is depicted in [Figure 1](#).

Figure 1 Study Schema

ICS=inhaled corticosteroid; Q4W=every 4 weeks; SC=subcutaneous.

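### The QTcF difference from placebo is planned only at Weeks 26 and 54 with no baseline covariate named; adding Week 4 and a baseline-adjusted model is a minor, nearly free improvement

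*SAP*

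**What the plan says.** SAP 4.7.4 (ECG Results) treats the ECG visits in two tiers.

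- **Descriptive tier.** Abnormal findings at "screening, run-in (Week 0), randomization (Week 2), Week 4, Week 26, and Week 54 will be summarized". For QTcF, PR, QRS and heart rate, "the values at each timepoint as well as changes from randomization will be summarized descriptively". QTcF outlier categories are given by visit and at any time. Week 4 is covered by all of these.
- **Comparative tier.** "The difference in mean QTcF change from randomization between each MSTT1041A arm and placebo" is to be reported, and "the corresponding 2-sided 90% CI will be summarized for Week 26 and Week 54". Week 4 is not in this list. No model and no covariate are named.

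The general covariate rule in SAP 4.5 applies to efficacy endpoints only, so it does not reach QTcF. The FEV1 model in SAP 4.5.2, by contrast, does include the baseline value.

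On timing, SAP Section 2 has study drug given "at the randomization visit (Week 2), Week 6, and every 4 weeks thereafter through Week 50", and the notes to Protocol Appendix 1 say: "On treatment days, all assessments should be performed prior to dosing, unless otherwise specified". ECGs after the first dose are scheduled at Weeks 4, 26, 54 and 70, and at an early termination visit four weeks after the last dose. Protocol 5.1.1.5 states the purpose of the ECGs: "To observe for any immediate cardiovascular toxicity, ECGs will be monitored (in triplicate".

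**The concern.** The only comparative QTcF estimate uses two visits at the end of a dosing interval; SAP 4.6 labels the drug concentrations at those same visits as Cmin. The one scheduled ECG taken nearer a dose is left out of it. The first placebo-controlled QTcF estimate therefore comes 24 weeks after first dosing, although the protocol's stated reason for ECGs is immediate toxicity.

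Week 4 has a further merit that does not depend on kinetics. It precedes the second dose at Week 6, so a patient dosed at randomization cannot yet have missed a dose. By Weeks 26 and 54, patients who stopped drug but stayed in follow-up remain in their arm, which could dilute an on-drug effect. The documents give no figure for how many that would be.

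With no covariate named, the natural reading is a simple difference in mean change. That gives a wider interval than a model using the randomization QTcF, which is already collected. What is at stake is completeness and some precision in a safety table; no hypothesis test depends on it.

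**Working it through.** The documents give no QTcF standard deviation, correlation, margin or power, so there is no stated figure to reproduce.

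**1. Timing (nominal visit weeks).** Doses at Weeks 2, 6, ..., 50 give (50 − 2)/4 + 1 = 13 doses, which agrees with Protocol 3.3.2: "Treatment will be given Q4W for 1 year, for a total of 13 doses". ECGs on dosing days come before the dose, so:

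| ECG visit | Last earlier dose | Weeks since that dose | Doses received | Placebo difference and CI planned |
|---|---|---|---|---|
| Week 4 | Week 2 | 2 | 1 | no |
| Week 26 | Week 22 | 4 | 6 | yes |
| Week 54 | Week 50 | 4 | 13 | yes |
| Week 70 | Week 50 | 20 | 13 | no |

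The early termination ECG is also four weeks after the last dose. Week 4 is thus the only scheduled post-dose ECG nearer a dose.

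**2. Does nearer a dose mean higher exposure?** Assume linear, one-compartment decline with absorption time ignored, and k = ln 2 / half-life. The concentration 14 days after one dose is proportional to exp(−14k). The steady-state trough with a 28-day interval is proportional to exp(−28k)/(1 − exp(−28k)). Their ratio is exp(14k) − exp(−14k) = 2 sinh(14k). The documents give no half-life, so a range is shown:

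| Assumed half-life (days) | Week 4 level / steady-state trough |
|---|---|
| 7 | 3.75 |
| 14 | 1.5 |
| 20 | 1.0 |
| 25 | 0.8 |

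The ratio equals 1 when k = asinh(0.5)/14, a half-life of about 20.2 days. Counting the actual number of doses changes little: at a 28-day half-life, Week 26 and Week 54 levels are 1.39 and 1.41 times the Week 4 level.

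**3. Precision.** Let r be the correlation between randomization and on-treatment QTcF, with equal SD at both visits. For n per arm, the 90% half-width is

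- change score: 1.645 × SD × √(2(1 − r)) × √(2/n)
- ANCOVA: 1.645 × SD × √(1 − r²) × √(2/n)

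The variance ratio, ANCOVA to change score, is (1 − r²)/(2(1 − r)) = (1 + r)/2, whatever SD and n are. The example uses n = 106 (125 per arm less the 15% dropout assumed in SAP 2.2: 125 × 0.85 = 106.25). SD = 15 ms is an assumption.

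| Assumed r | ANCOVA interval narrower by | Half-width, change score (ms) | Half-width, ANCOVA (ms) |
|---|---|---|---|
| 0.5 | 13.4% | 3.39 | 2.94 |
| 0.6 | 10.6% | 3.03 | 2.71 |
| 0.7 | 7.8% | 2.63 | 2.42 |
| 0.8 | 5.1% | 2.14 | 2.03 |
| 0.9 | 2.5% | 1.52 | 1.48 |

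The algebra gives change-score to ANCOVA width ratios of 1.155, 1.085 and 1.026 at r = 0.5, 0.7 and 0.9. A simulation with 106 per arm and 1,000 runs gave mean standard-error ratios of 1.152, 1.082 and 1.025.

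**The case against.** The case for leaving the plan alone has real content.

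- **Week 4 data are not lost.** They appear by arm in the descriptive and outlier tables. If those tables print n, mean and SD, a reader can work out the unadjusted Week 4 difference and interval.
- **Immediate toxicity is handled elsewhere.** Protocol 4.5.9 and 5.1.2.3 set patient-level QTcF procedures, and the iDMC reviews unblinded ECG data about every three months (Protocol 3.1.2). An ECG two weeks after a dose is not immediate either.
- **Weeks 26 and 54 are a coherent choice.** They follow repeated dosing, and SAP 4.6 lists a concentration sample at both. Week 4 is not on that list; it is sampled only in the subset of about 80 patients (Protocol Appendix 2). The SAP does not give this as its reason.
- **Nothing formal depends on the interval.** There is no QTcF margin, hypothesis or power statement. In the example above the half-width changes by only 0.04 to 0.45 ms.

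All of this lowers the importance of the point. None of it shows a drawback to the extra row or the covariate.

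Two stronger readings are tempting, and the documents support neither. A reader might infer that Weeks 26 and 54 are the visits least able to show a QTcF effect. That would need a half-life below about 20 days, and none is given; with a longer one, exposure is higher at the later visits. A reader might also infer that baseline is ignored. It is not: change from randomization already subtracts it, and the SAP names no model rather than ruling out a covariate.

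**Conclusion.** The point holds as a minor improvement to a safety display, not as an error in the plan. The omission of Week 4 from the placebo comparison follows directly from the text and the schedule, and needs no assumption. It is the stronger half of the point, because Week 4 is the only scheduled post-dose ECG within four weeks of a dose and is least affected by treatment discontinuation. Its pharmacological value is uncertain, because Week 4 exposure is above the later troughs only for half-lives under about 20 days, assuming linear kinetics. Early exposure (Week 4) and accumulated exposure (Weeks 26 and 54) are complementary, so all three visits should be reported.

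The precision gain from the covariate is real for any correlation below 1 but modest: intervals about 13% narrower at r = 0.5 and about 3% narrower at r = 0.9. These correlations are assumed, with equal SD at both visits.

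**What to change.** In SAP 4.7.4:

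1. Add Week 4 to the visits at which the QTcF difference from placebo and its 2-sided 90% CI are reported, keeping Weeks 26 and 54.
2. Name the estimator: ANCOVA at each visit with randomization QTcF as covariate. Alternatively, use a repeated-measures model over Weeks 4, 26 and 54 with treatment, visit, treatment by visit, randomization QTcF and its interaction with visit, parallel to the FEV1 model in SAP 4.5.2.

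The cost is one more visit in one table and a standard model. The ECGs are already scheduled, and no visit, procedure or patient-management rule changes. SAP Section 1 allows no changes at or after the 54-week primary analysis, so the edit has to be made before then.

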For safety monitoring purposes, the investigator must review, sign, and date all ECG tracings. Paper copies of ECG tracings will be kept as part of the patient's permanent study file at the site. Digital recordings will be stored at a central ECG laboratory. The following should be recorded: heart rate, RR interval, QRS interval, PR duration, uncorrected QT interval, and QTcF based on the machine readings of the individual ECG tracings. Any morphologic waveform changes or other ECG abnormalities must be documented. If considered appropriate by the Sponsor, ECGs may be analyzed retrospectively at a central laboratory.

If at a particular postdose timepoint, the mean QTcF is >500 ms and/or > 60 ms longer than the value at the randomization visit, another ECG must be recorded, ideally within the next 5 minutes, and ECG monitoring should continue until QTcF has stabilized on two successive ECGs. The same procedure (i.e., triplicate ECGs) should be repeated approximately 30 minutes after QTcF has stabilized on two successive ECGs of the first measurement. The Medical Monitor should be notified. Standard-of-care

treatment may be instituted per the discretion of the investigator. If a PK sample is not scheduled for that timepoint, an unscheduled PK sample should be obtained. A decision on study drug discontinuation should be made, as described in Section 5.1.2.3. The investigator should also evaluate the patient for potential concurrent risk factors (e.g., electrolyte abnormalities, co-medications known to prolong the QT interval, severe bradycardia).

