5.1.2.3 Management of Increases in QT Interval

Study drug should be discontinued in patients who develop any of the following, unless there is a clear alternative cause for the changes:

- Sustained (at least two ECG measurements >30 minutes apart) QTcF that is >500 ms and >60 ms longer than the baseline value
- Sustained absolute QTcF that is >515 ms
- An episode of torsades de pointes or a new ECG finding of clinical concern

Of note, if there is a new intraventricular conduction block, the increase in QRS complex duration should be subtracted from the QTcF change, because this represents an

increase in QTcF unrelated to alterations in repolarization. Also of note, it is not uncommon to record arrhythmias such as non-sustained ventricular tachycardia, supraventricular tachycardia, pauses, or atrial fibrillation in healthy volunteers receiving placebo during periods of extended ECG monitoring. Therefore, it is critical that expert cardiology advice be sought to confirm any ECG changes and to ascertain the likelihood of a drug-induced arrhythmia versus the background occurrence of this arrhythmia. In such a situation, saving all available ECG data is highly suggested.

Management of patients with sustained QTcF prolongation should include close monitoring, with ECGs repeated at least hourly until two successive ECGs show resolution of the findings, correction of any electrolyte abnormalities, and possible discontinuation of other concomitant medications that are known to prolong the QT interval. Consultation with a cardiologist or electrophysiologist is recommended, to help in the management of such patients.

In rare circumstances, it may be acceptable to resume study drug, provided that any ECG abnormalities have resolved and the patient is appropriately monitored. Clinical judgment should be applied.

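### SAP 4.7.4 does not report QTcF against the protocol's own thresholds: women have no >500 ms row, and the any-time summary separates neither >500 ms nor a >60 ms increase for either sex

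*SAP*

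**What the plan says.** **Protocol.** Section 4.5.9 (Electrocardiograms) requires repeat ECGs, monitoring, notice to the Medical Monitor and a PK sample if "the mean QTcF is >500 ms and/or > 60 ms longer than the value at the randomization visit". Section 5.1.2.3 gives the discontinuation criteria, which apply unless there is a clear alternative cause. One is a sustained "QTcF that is >500 ms and >60 ms longer than the baseline value". Another is a sustained absolute value above 515 ms. None of these differs by sex.

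**SAP 4.7.4.** By visit, the absolute cut-offs are ">450, >480, or >500 ms for males or >470, >490, or >510 ms for females". Also by visit and for both sexes, "an increase from randomization in QTcF of >30 and >60 ms will be summarized". A separate any-time summary uses 450 ms for men, 470 ms for women, or "a QTcF increase from baseline of > 30 ms at any time during the study".

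**Laboratory panels.** Protocol 5.1.1.5 discusses metabolic or cardiovascular effects as a potential risk and says that, with fasting glucose and HbA1c, "lipid panels will be monitored to observe and/or identify any effects of MSTT1041A on cardiovascular risk factors". Protocol 4.5.14 lists these tests apart from the chemistry panel. SAP 4.7.3 says descriptive summaries "will be generated for hematology, chemistry, and urinalysis parameters".

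**The concern.** An outlier table in a safety report should let the reader see how many patients in each arm crossed the values that the protocol itself treated as needing action. Here the tabulated bands and the protocol thresholds coincide for men at 500 ms and, by visit, for a 60 ms increase. They do not coincide for women on the absolute value. They coincide for neither sex in the any-time summary, which is where a worst-case count would be looked for.

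This matters more than usual because cardiovascular effects are a potential risk named in the protocol, and ECG monitoring was put in place to watch for them. The laboratory point is of the same kind but weaker: three tests are collected for that named risk, and the section that specifies laboratory output does not name them.

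**Working it through.** The documents give no figure to reproduce. The check compares the protocol's thresholds with the rows the SAP will produce.

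**QTcF**

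| Protocol threshold (both sexes) | SAP by visit, men | SAP by visit, women | SAP any-time |
|---|---|---|---|
| Above 500 ms | Row present | No row (470, 490, 510) | Not separated (450/470) |
| Increase above 60 ms | Row present | Row present | Not separated (30) |
| Above 500 ms and increase above 60 ms | No joint row | No joint row | No joint row |
| Above 515 ms | No row | No row | No row |

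**What can be recovered for women at one visit.** Write N(>x) for the number of women above x ms in an arm. The planned rows give only

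N(>510) ≤ N(>500) ≤ N(>490).

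The width of that range is N(>490) − N(>510), the number of women at 491 to 510 ms. That band mixes women at 501 to 510 ms, who meet the monitoring trigger on the absolute value, with women at 491 to 500 ms, who do not. The count is exact only if the band is empty.

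**What can be recovered for any time.** A man above 500 ms is also above 450 ms, a woman above 500 ms is also above 470 ms, and a rise above 60 ms is also above 30 ms. Every such patient is therefore inside the any-time summary. The any-time figures give an upper limit, and a zero there would show that nobody crossed. The largest single-visit count gives a lower limit. If the upper limit is above zero, the tables generally do not give the number itself.

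**Joint condition.** Even where both single rows exist (men, by visit), the joint count is known only to be no larger than the smaller of the two.

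**Laboratory**

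| Collected (Protocol 4.5.14) | In the protocol's chemistry panel? | Named in SAP 4.7.3? |
|---|---|---|
| Fasting lipids | No | No |
| HbA1c | No | No |
| Fasting glucose | Glucose is listed; the fasting test is a separate item | No |

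The open-ended wording in SAP 4.7.3 belongs to the WHO-grade summary of selected parameters. It does not extend the sentence that lists hematology, chemistry and urinalysis.

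**The case against.** The case against has several fair parts.

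- **Nobody is lost.** A reader might infer that an excursion above 500 ms or 60 ms outside a tabulated visit would appear in no summary. That is wrong. It falls in the any-time summary, undistinguished, and women above 500 ms are in the >490 ms row. What is missing is the separate count.
- **The 60 ms increase is already tabulated** by visit for both sexes. The gap for that threshold is confined to the any-time summary.
- **The protocol has two rules, not one.** The monitoring trigger in 4.5.9 is *and/or*. The discontinuation criterion in 5.1.2.3 is sustained and joint, with 515 ms as an alternative. Single >500 ms and >60 ms rows speak to the first rule. They do not count patients who meet the second.
- **The sex-specific bands have a source.** The lowest pair, 450/470 ms, matches the entry exclusion in Protocol 4.1.2.1, and the choice of outlier bands is a reporting decision. This explains the existing rows and is a reason to keep them. It does not supply the count at 500 ms.
- **Other safeguards exist.** ECG deterioration that leads to a treatment change or discontinuation is an adverse event, and events leading to discontinuation are summarized. The SAP also covers MACE, mean QTcF differences from placebo with 90% CIs, and shifts in ECG findings. The iDMC sees unblinded ECG and laboratory data about every 3 months. These limit the consequences, but none gives the number of patients past the monitoring threshold.
- **On the laboratory tests,** a reader might infer that they have no planned output and no comparison by arm. The SAP does not support that. Section 4.7 says safety summaries will include the outcomes in 2.1.4, which lists change from baseline in clinical laboratory results, and that summaries are by arm. Glucose is also in the chemistry panel. What remains is that 4.7.3 does not name the tests.

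**Conclusion.** The QTcF point holds. As written, SAP 4.7.4 cannot give an exact count of women above 500 ms at a visit unless the 491 to 510 ms band is empty. Nor does it separately count patients of either sex who were ever above 500 ms or 60 ms. The joint condition appears in no row. The shortfall is in resolution: affected patients are in the tables but cannot be told apart from others.

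The laboratory point is secondary: a general promise of laboratory summaries in 2.1.4 and 4.7, against a narrower list in 4.7.3.

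Both are minor. They concern descriptive safety reporting and leave alpha, power and the efficacy analyses unchanged. The number of patients affected cannot be estimated from the documents. The conclusion assumes that *chemistry* in SAP 4.7.3 means the panel the protocol defines, and that no table specification outside these documents already adds the rows. It takes no position on which QTcF threshold is clinically right; the protocol and SAP passages need to be reconciled.

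**What to change.** In SAP 4.7.4:

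1. Add a >500 ms row for both sexes to the by-visit table and keep the existing sex-specific rows.
2. Add three counts by arm to the any-time summary, for both sexes: above 500 ms, increase above 60 ms, and both together.
3. State which readings enter the any-time counts. SAP 4.7.4 keeps only the last three ECGs when a visit has more than three, while Protocol 4.5.9 orders repeats once the trigger is crossed. If repeats are filed under the same visit, the triggering readings could drop out.

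These rows would still not count the sustained or 515 ms criteria, and a footnote should say so.

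In SAP 4.7.3, name fasting lipids, fasting glucose and HbA1c among the parameters summarized by arm with change from baseline.

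The cost is a few table rows from data already collected, with no change to any clinical rule, visit or sample. SAP Section 1 allows no changes at or after the 54-week analysis, so the edit belongs before that point; rows added later would be post hoc.
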